6.2.2 Bladder Stress Test (BST)

Before the BST, a bladder scan will be performed by ultrasound to verify that the subject's bladder contains at least 150 ml of urine. The volume of urine present in the bladder should be captured. Once the urine volume has been determined, the subject will stand over an absorbent pad and be instructed to cough forcefully and/or perform a Valsalva maneuver to elicit a urinary stress leak. If there is no observable urine loss on the absorbent pad, a paper towel will be placed lightly against the perineum to detect any urine leakage that may not have dropped onto the pad. Any urine loss observed by the research staff is indicative of a positive BST.

After completion of the BST, subjects will be asked to void and the volume of urine remaining in the bladder after voiding (post void residual) will be measured via ultrasound bladder scan. The volume of urine present in the bladder post voiding should be captured.

A BST will be conducted for each subject at the Screening Visit and at Visit 5 (Table 12–1).

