4.1.1 Inclusion Criteria

Each subject must meet all of the following criteria to be enrolled in this study:

1. Able to read, understand, and provide written, dated, informed consent prior to screening, and be likely to comply with study protocol and communicate with study personnel about AEs and other clinically important information.
2. Female, 18 to 80 years of age, inclusive, at screening
3. Subjects must have undergone spontaneous, medically induced, or surgical menopause prior to the start of this study. Postmenopausal subjects are defined as those subjects who meet one of the following criteria:
 - a) greater than or equal to 12 months of spontaneous amenorrhea, or;
 - b) at least 6 months of spontaneous amenorrhea with serum follicle stimulating hormone levels > 40 mIU/ml, or;
 - c) at least 6 weeks postsurgical bilateral oophorectomy with or without hysterectomy, or;
 - d) subjects 60 years of age or older with previous hysterectomy without an oophorectomy with serum follicle stimulating hormone levels > 30 mIU/ml, or;
 - e) subjects less than 60 years of age with previous hysterectomy without an oophorectomy with serum follicle stimulating hormone levels > 40 mIU/ml.
4. SUI symptoms of at least 6 months duration

5. Predominant SUI as determined at the Screening Visit using the MESA incontinence questionnaire.
6. 24-Hour pad weight > 3 g during the screening period
7. A minimum of 1 and no more than 15 SUI episodes on any single day AND no fewer than 9 total SUI episodes over 3 days as reported in the 3-day voiding diary, determined during the screening period
8. Serum alanine aminotransferase (ALT) or aspartate aminotransferase (AST) levels < 1.5 times the upper limit of normal at the Screening Visit (Note: laboratory values falling outside of prespecified ranges may be retested once at the discretion of the investigator. Results of the retest must be within prespecified ranges and must be available prior to the baseline visit)
9. Positive bladder stress test (BST) conducted during the Screening Visit
10. Subject agrees not to start any new treatment (medication or otherwise) during the treatment and follow-up periods, including vaginal rejuvenation, that is known or suspected to affect lower urinary tract function.
11. Subject agrees to discontinue use of bladder support devices, including but not limited to vaginal pessary, during the screening, treatment, and follow-up periods.

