7.2 Secondary Efficacy Endpoints

The secondary efficacy endpoints in this study are the following assessments compared to baseline at each visit during the treatment period:

- Responder rate, where a responder is defined as having a $\geq 50\%$ reduction compared to baseline in the mean number of stress incontinence episodes per day as assessed by the 3-day voiding diary
- Change in the number of stress incontinence episodes per day as measured by the 3-day voiding diary
- Change in the total number of voids per day as measured by the 3-day voiding diary
- Change in the mean number of stress incontinence episodes per day as measured by the 3-day voiding diary
- Change in 24-hour pad weight as measured by the 24-hour pad weight test
- Change in the results of the Bladder Stress Test (BST)
- Change in subject-reported impression of SUI severity as measured by the PGI-S
- Change in subject-reported impression of SUI improvement as measured by the PGI-I
- Change in subject-reported urogenital distress as measured by the UDI-6
- Change in subject-reported impact of urinary incontinence on daily life as measured by the IIQ-7 Short Form

- Change in subject-reported impact of urinary incontinence on daily life as measured by the I-QOL
- Change in subject-reported sexual function as measured by the FSFI
- Change in subject-reported assessment of fecal incontinence as measured by the Vaizey Incontinence Severity Score.
- Change in subject-reported stress incontinence, urge incontinence, and mixed incontinence as measured by the MESA incontinence questionnaire (Week 12 only)

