7.7.2 Analysis of Secondary Efficacy Endpoints

For binary secondary endpoints (responders), the treatment effect will be estimated using a logistic regression model with treatment as a covariate.

For continuous secondary endpoints, treatment effects will be estimated using a mixed model repeated measures analysis (MMRM). The MMRM model will specify an unstructured variance/covariance matrix and include treatment group, visit, and baseline as covariates.

For ordinal endpoints, treatment effects will be estimated using a proportional odds model.

Further details on the analysis of secondary efficacy endpoints will be provided in the SAP.

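### A negative Bladder Stress Test at Week 12 can be recorded after a single manoeuvre that is not documented, which inflates conversion in every arm and dilutes the treatment difference on this secondary endpoint

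*Combined protocol and SAP*

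**What the plan says.** Section 6.2.2 describes the BST. A bladder scan is done first to "verify that the subject's bladder contains at least 150 ml of urine". This is a floor, with no target or ceiling. The subject then stands over a pad and is to "be instructed to cough forcefully and/or perform a Valsalva maneuver to elicit a urinary stress leak". No number or order of efforts is given. If nothing is seen on the pad, a paper towel is held to the perineum. The result is yes or no: "Any urine loss observed by the research staff is indicative of a positive BST".

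Pre-test volume is recorded: "The volume of urine present in the bladder should be captured". The section does not ask staff to record the manoeuvre.

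On timing, "A BST will be conducted for each subject at the Screening Visit and at Visit 5". Visit 5 is Week 12. Section 4.1.1, criterion 9, requires a "Positive bladder stress test (BST) conducted during the Screening Visit", and Section 4.1 allows no deviation from the entry criteria. Change in BST is a secondary efficacy endpoint (Sections 2.2 and 7.2). For binary secondary endpoints, Section 7.7.2 says "the treatment effect will be estimated using a logistic regression model with treatment as a covariate". It leaves further detail to a separate SAP, whose text is not part of the document reviewed here.

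**The concern.** A yes/no provocation test can miss leaks. How many it misses depends on how hard the woman is provoked and how full her bladder is. Section 6.2.2 lets both vary. One woman may be called negative after one forceful cough at 150 ml, another only after a cough and a Valsalva at a much larger volume.

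Because every eligible woman starts positive, her result can change only to negative. A leak missed at Week 12 is therefore always counted as a conversion, and no error in the other direction offsets it. If this happens at a similar rate in each arm, the conversion rate rises everywhere, including on placebo, and the gap between arms narrows. A real effect on this endpoint becomes harder to detect, and the within-arm conversion rates are hard to interpret. If the manoeuvre is not recorded, no later analysis can separate thorough tests from single-manoeuvre tests.

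**Working it through.** **What drives the arm comparison.** Baseline BST is positive for every eligible woman, so it is a constant. Change in BST is then the same variable as Week 12 BST, and a logistic model with treatment alone compares Week 12 status between randomized arms. How strongly a woman was provoked at screening does not enter that comparison. The relevant quantity is the sensitivity of the Week 12 test.

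**The plan's own figure.** Section 7.4 sizes the trial on the diary responder endpoint, not on the BST. With 60% vs 40%, two-sided 5% and 80% power, the pooled two-proportion formula gives 97 per arm. Allowing for 25% discontinuation, 97 / 0.75 = 129.3, rounded up to 130, or 390 in total. This agrees with the stated figure of approximately 400. No BST rate or BST power is stated.

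**Inputs for the illustration.**
- From Section 7.4: 400 / 3 = 133 per arm, less 25%, gives 100 tested per arm; two-sided 5% per pairwise comparison.
- Assumed, because the documents give none: a share *p* truly still positive at Week 12, 0.80 on placebo and 0.60 on active; a share *q* of women given a weaker test; and the proportion *s* of true leaks which that test detects. *q* and *s* are taken as equal in all arms, and false positives are ignored.

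**Formulas.**
- Observed positive rate = *p* × *k*, where *k* = 1 − *q*(1 − *s*).
- Observed difference = 20 points × *k*.
- Power = Φ(difference / SE − 1.96), with SE = √{[P₀(1 − P₀) + P₁(1 − P₁)] / 100}, where P₀ and P₁ are the observed placebo and active rates.

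**Worked case, *q* = 0.50, *s* = 0.60.** *k* = 1 − 0.50 × 0.40 = 0.80. Observed rates are 0.64 and 0.48, a difference of 0.16. SE = √[(0.2304 + 0.2496) / 100] = 0.0693. 0.16 / 0.0693 = 2.31, and 2.31 − 1.96 = 0.35, so power is 63.7%.

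| *q* | *s* | *k* | Positive, placebo | Positive, active | Placebo converted | Difference (points) | Power |
|---|---|---|---|---|---|---|---|
| 0 | – | 1 | 80% | 60% | 20% | 20 | 88.5% |
| 0.10 | 0.75 | 0.975 | 78% | 58.5% | 22% | 19.5 | about 86% |
| 0.25 | 0.75 | 0.9375 | 75% | 56.25% | 25% | 18.75 | 81.3% |
| 0.50 | 0.75 | 0.875 | 70% | 52.5% | 30% | 17.5 | 73.3% |
| 0.50 | 0.60 | 0.80 | 64% | 48% | 36% | 16 | 63.7% |

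With a pooled variance, the first and last rows become 87.6% and 62.7%, so the choice of approximation does not matter here. On the odds-ratio scale that the protocol would report, the effect for conversion falls from 2.67 (40% vs 20%) to 1.93 (52% vs 36%).

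**The case against.** The strongest reply is that much of the test is already fixed at both visits: a scanned minimum volume, a standing position, a forceful effort, and a paper-towel check whenever the pad shows nothing. Volume is captured, and the SAP may use it. The trial is randomized and double-blind, so any loss of sensitivity should fall equally on the arms. The BST is one of more than a dozen secondary endpoints, and the trial was not sized on it. All of this stands. It limits the point to dilution of a secondary endpoint and makes it minor. It does not remove the point, because a SAP cannot change how sites perform a test or recover a manoeuvre that nobody recorded.

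A reader might also draw three stronger conclusions, which the documents do not support.

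- **That mismatch between the screening and Week 12 tests distorts the arm comparison.** It does not, because a constant baseline drops out. Requiring the two tests to match would address something that the comparison does not use.
- **That the Week 12 test will be the weaker one, since a positive is needed to enrol and nothing requires one later.** No text supports this. The opposite is as plausible: at screening, a leak on the first cough already settles the result, while at Week 12 a woman who stays dry may be provoked further.
- **That the error favours the drug.** Nothing in the documents suggests that provocation differs by arm, and without that the effect is dilution.

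**Conclusion.** The point holds as a minor, cheaply corrected weakness. Section 6.2.2 permits a less sensitive Week 12 test than the same staff could perform with the same equipment. Any leaks missed for that reason raise apparent conversion to negative in every arm and reduce the difference on change in BST. The primary diary endpoint and its sample size are unaffected.

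The size cannot be determined from the documents. Under the assumed rates and a common sensitivity across arms, the loss of power runs from about 3 points (a tenth of women, 75% detection), through about 7 points (a quarter, 75% detection), to about 25 points (half, 60% detection). The last figure needs half of all women to receive a test that misses two leaks in five. It is the far end of an illustration, not a forecast.

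**What to change.** In Section 6.2.2, replace the and/or option with a rule that both a forceful cough and a Valsalva, with the paper-towel check already described, must be completed before a negative BST is recorded, at either visit. A leak on the first manoeuvre can still end the test as positive. Add a field for the manoeuvre or manoeuvres performed, so that the rule can be verified.

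For volume, use the pre-test value already captured at Week 12 as a covariate in a sensitivity analysis of the BST endpoint. It should stay a sensitivity analysis, because Week 12 volume is measured after randomization. This is preferable to a volume band with refilling and retesting, which would need a width that the documents give no basis for and would lengthen a full Visit 5.

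The cost is a change of wording and site instructions, one added data field, and a slightly longer test for women who do not leak on the first manoeuvre. At screening, the rule could also turn a few single-manoeuvre negatives into positives, so a few more women might meet criterion 9.

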6.2.3 Patient Global Impression of Severity

The PGI-S is a global rating of subject-reported impression of SUI severity using a 4-point scale (Appendix 12.3). Validity of the PGI-S has been established for application in SUI.

6.2.4 Patient Global Impression of Improvement

The PGI-I is a global rating of subject-reported impression of SUI improvement using a 7-point scale (Appendix 12.4). Validity of the PGI-I has been established for application in SUI.

6.2.5 Urogenital Distress Inventory and Incontinence Impact Questionnaire Short Form

The UDI-6 (Appendix 12.5) and IIQ-7 Short Form (Appendix 12.6) are validated subject questionnaires used to assess symptom distress and the impact of urinary incontinence on daily life (Shumaker et al 1994; Uebersax et al 1995). The UDI-6 and IIQ-7 are both “A

grade” recommended by the Fourth International Consultation on Incontinence (Shumaker et al 1994; Uebersax et al 1995; Staskin et al 2008, 2009).

6.2.6 Incontinence Quality of Life

The I-QOL (Appendix 12.7) is a validated subject questionnaire used to assess the impact of urinary incontinence and treatments.

6.2.7 Female Sexual Function Index

The FSFI (Appendix 0) is a self-administered questionnaire to assess overall sexual experience that consists of 19 questions scored from 0 to 5. The scale contains 6 domains: desire, arousal, lubrication, orgasm, satisfaction, and pain (Rosen et al 2000). The FSFI total score is a weighted average of the 6 domains with each contributing a maximum of 6 points to the total (maximum score of 36).

6.2.8 Vaizey Incontinence Severity Score

The Vaizey Incontinence Severity Score is obtained through a self-administered questionnaire to assess a subject’s bowel symptoms and the impact if these symptoms of daily life.

6.2.9 Twenty-Four Hour Pad Weight Test

The 24-hour pad weight test is a quantitative test intended to provide information on the severity of incontinence. The amount of urine leaked over the 24 hours of testing is quantified by measuring the change in weight of perineal pads used during testing.

The 24-hour pad test should be completed during 1 day of each scheduled 3-day voiding diary. Subjects will be instructed to record pad weight on a day that is typical for them in terms of activity level and fluid intake. Subjects must use the incontinence pads provided in the 24-hour pad weight test kit for the 24-hour test; no other pads are to be used. Subjects should receive 8 incontinence pads for use during each 24-hour test period. Pads will be returned before or at the next scheduled study visit.

6.2.10 Medical, Epidemiological, and Social Aspects of Aging Questionnaire

The MESA incontinence questionnaire (Appendix 12.2) consists of 15 items divided into stress incontinence (9 items) and urge incontinence (6 items) subscales. Based on their responses, subjects can be characterized as having predominant stress incontinence, urge incontinence, or mixed incontinence (Herzog and Fultz 1990).

6.3 Safety Assessments

6.3.1 Adverse Events

6.3.1.1 Definitions of Adverse Events

The investigator is responsible for reporting all AEs that are observed or reported during the study regardless of their possible relationship to study drug or their clinical significance.

An AE is defined as any untoward medical occurrence in a subject enrolled into this study regardless of its causal relationship to study drug. Subjects will be instructed to contact the investigator at any time after randomization if any symptoms develop.

A treatment-emergent AE (TEAE) is defined as any event not present before exposure to study drug or any event already present that worsens in either intensity or frequency after exposure to study drug and within the 30 days following discontinuation of drug treatment

An SAE is defined as any event that results in one of the following conditions:

- Death
- Life-threatening event (defined as a subject at immediate risk of death at the time of the event)
- An event requiring inpatient hospitalization or prolongation of existing hospitalization
- An event that results in persistent or significant disability/incapacity
- An event that results in a congenital anomaly/birth defect

- Any other important medical event that may not result in death, be life threatening, or require hospitalization may be considered an SAE when, based upon appropriate medical judgment, the event may jeopardize the subject or may require medical or surgical intervention to prevent one of the outcomes listed in this definition. Examples of such medical events include allergic bronchospasm requiring intensive treatment in an emergency room or at home, blood dyscrasias or convulsions that do not result in inpatient hospitalization, or the development of drug dependency or drug abuse.

6.3.1.2 Eliciting and Documenting Adverse Events

Adverse events will be assessed beginning at enrollment (date of signed informed consent) through the completion of the durability or follow up period.

Serious AEs that occur more than 30 days after the last dose of study drug need not be reported unless the investigator considers them to be related to study drug.

At every study visit, subjects will be asked a standard nonleading question to elicit any medically related changes in their well-being. They will also be asked if they have been hospitalized, had any accidents, used any new medications, or changed concomitant medication regimens (both prescription and OTC medications).

In addition to subject observations, AEs identified from any study data (e.g., laboratory values, physical examination findings, electrocardiogram [ECG] changes) or identified from review of other documents (e.g., subject diaries) that are relevant to subject safety will be documented on the AE page in the eCRF.

6.3.1.3 Reporting Adverse Events

All AEs reported or observed during the study will be recorded on the AE page in the eCRF. Information to be collected includes drug treatment, dose, event term, time of onset, investigator-specified assessment of severity and relationship to study drug, time of resolution of the event, seriousness, any required treatment or evaluations, and outcome. Adverse events resulting from concurrent illnesses, reactions to concurrent illnesses, reactions to concurrent medications, or progression of disease states must also be reported. All AEs will be followed to adequate resolution. The Medical Dictionary for Regulatory Activities (MedDRA) will be used to code all AEs.

Any medical condition that is present at the time that the subject is screened should not be reported as an AE. However, if a pre-existing condition changes in intensity or frequency at any time during the study, it should be recorded as an AE.

Any AE that meets SAE criteria (Section 6.3.1.1) must be entered into the electronic data capture (EDC) system immediately (i.e., within 1 business day) after site personnel first learn of the event. Once the qualifying SAE data are entered, pharmacovigilance will be notified by an email alert, which will contain high level safety information. Additional safety information will be obtained from the EDC system via applicable eCRF pages. If the EDC system is not available, the site should send a completed paper SAE report form to pharmacovigilance by fax or email:

- Safety Fax Line: [name] (US toll-free)
- Safety Email: [contact]

When the EDC system is again available, the site must enter all applicable information into the EDC system. All supporting source information concerning the SAE (e.g., hospital records) should be provided by fax or email.

If there is a question concerning an SAE, the site needs guidance regarding reporting of an SAE, the site is returning a call from a safety specialist, or the site urgently needs to report an SAE or make pharmacovigilance aware of an SAE, the Safety Hotline should be used:

- Safety [contact] (US toll free)

If a site makes an initial report of an SAE by the safety hotline, the site must subsequently enter all applicable information into the EDC system immediately thereafter.

6.3.1.4 Assessment of Severity

All AEs will be assessed by the Investigator according to NCI-CTCAE, Version 4.0. For any AE that is not specifically covered in NCI-CTCAE, Version 4.0, the criteria below should be used:

Grade	Description
0	No AE or within normal limits
1	Mild; asymptomatic or mild symptoms; clinical or diagnostic observations only; intervention not indicated
2	Moderate; minimal, local, or non-invasive intervention indicated; limiting age-appropriate instrumental activities of daily living
3	Severe or medically significant but not immediately life-threatening; hospitalization or prolongation of hospitalization indicated; disabling; limiting self-care activities of daily living
4	Life-threatening consequences; urgent intervention indicated

Changes in the severity of an AE should be documented to allow an assessment of the duration of the event at each level of intensity to be performed. Adverse events characterized as intermittent do not require documentation of onset and duration of each episode.

6.3.1.5 Assessment of Causality

The investigator's assessment of an AE's relationship to study drug is part of the documentation process, but it is not a factor in determining what is or is not reported in the study. If there is any doubt as to whether a clinical observation is an AE, the event should be reported.

The relationship or association of the test article in causing or contributing to the AE will be characterized using the following classification and criteria:

- Unrelated:** This relationship suggests that there is no association between the study drug and the reported event.
- Possible:** This relationship suggests that treatment with the study drug caused or contributed to the AE, i.e., the event follows a reasonable temporal sequence from the time of drug administration or follows a known response pattern to the study drug but could also have been produced by other factors.
- Probable:** This relationship suggests that a reasonable temporal sequence of the event with drug administration exists and, based upon the known pharmacological action of the drug, known or previously reported adverse reactions to the drug or class of drugs, or judgment based on the investigator's clinical experience, the association of the event with the study drug seems likely. The event disappears or decreases on cessation or reduction of the dose of study drug.
- Definite:** This relationship suggests that a definite causal relationship exists between drug administration and the AE, and other conditions (concurrent illness, progression/expression of disease state, or concurrent medication reaction) do not appear to explain the event. The event reappears or worsens if the study drug is re-administered.

